7.2.5 Immune-mediated adverse events

Immune-mediated AE (IMAE) refers to specific events (including pneumonia, diarrhea/colitis, hepatitis, nephritis/renal dysfunction, rash, and endocrinopathy) related to immunosuppressive treatment. Endocrine events (hypothyroidism/thyroiditis, hyperthyroidism, hypophysitis, diabetes, and adrenal insufficiency) are often excluded, as they are usually unrelated to treatment and are usually managed in the absence of interventions with immunosuppressants. Preferred terms included in the IMAE analysis to support warnings and precautions are shown in [Table 11](#).

IMAE Type	PT included in IMAE (MedDRA)
Pneumonia	Pneumonia, interstitial pneumonia
Diarrhea/Colitis	Diarrhea, colitis, enterocolitis
Hepatitis	Hepatotoxicity, hepatitis, hepatitis acute, autoimmune hepatitis, AST increased, ALT increased, bilirubin increased, ALP increased
Adrenal Insufficiency	Adrenal Insufficiency
Hypothyroidism/thyroiditis	Acute thyroiditis (collapse due to frequent thyroiditis), autoimmune thyroiditis (collapse due to frequent thyroiditis)
Hyperthyroidism	Hyperthyroidism
Hypophysitis	Hypophysitis
Diabetes Mellitus	Diabetes mellitus, diabetic ketoacidosis
Nephritis and kidney dysfunction	Nephritis, hepatitis acute, tubulointerstitial nephritis, renal failure acute, renal failure, creatinine increased
Rash	Rash, maculo-papular rash

Table 11. Preferred terms included in the IMAE analysis to support warnings and precautions

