1.3. Potential Risks and Benefits

1.3.1. Known potential risks

Any investigational drug or treatment may have unpredictable or even serious side effects.

As of 25 Aug., 2017, a total of 539 patients with advanced cancer had been treated with SHR-1210 (either monotherapy or in combination with other drugs). Among them, 414 subjects (76.8%) reported ≥ 1 AE. The most common (incidence $> 5\%$) treatment-related AEs were hemangioma (64.7%), hemangioma of skin (25.0%), asthenia (9.3%), capillary disorder (8.3%), aspartate

aminotransferase increased (8.2%), pruritus (7.8%), rash (7.6%), alanine aminotransferase increased (6.7%), fever (6.5%), white blood cell count decreased (6.1%), anemia (5.9%), blood bilirubin increased (5.9%), hypothyroidism (5.6%), and conjugated bilirubin increased (5.0%). There were a total of 38 SAEs related to SHR-1210, mainly including hemangioma of skin (6 events), abnormal liver function (4 events), interstitial pneumonia (3 events), and infectious pneumonia (2 events).

Investigator-assessed immune-mediated AEs were predominantly skin toxicities (such as rash and capillary proliferation). Most immune-mediated AEs were grade 1-2 in severity. The above data was compared with adverse drug reactions reported for other approved anti-PD-1 antibodies - nivolumab from BMS and pembrolizumab from Merck. The incidence and severity were both low. Overall, the adverse drug reactions of this product are expected to be similar to those of nivolumab and pembrolizumab. Recommended management of common side effects and protocol-specified dose modifications have been established for this study, so that, in the presence of clinical benefit, subjects may continue the SHR-1210 treatment.

All monotherapies using anti-PD-1 antibodies outperformed conventional chemotherapy and targeted therapy in terms of adverse drug reactions on the whole. However, immune-related adverse reactions still require special attention, mainly including immune-related interstitial pneumonia, rash, thyroiditis, as well as those with lower incidence ($\leq 1\%$), such as vitiligo, colitis, nephritis, hepatitis, uveitis, adrenal insufficiency, and nerve paralysis. These immune-related adverse reactions are mostly mild and manageable. Very few are SAEs or potentially life-threatening. Thanks to established procedures for toxicity management, the majority of immune-mediated AEs can be adequately controlled.

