In the TEAE summary table, AE occurring after the study drug treatment will be analyzed by MedDRA system organ class (SOC) and preferred term (PT), and descriptive statistics will be provided by frequency and percentage. The summary table contains the number of subjects experiencing at least one TEAE, TEAEs leading to treatment withdrawal, SAEs, TEAEs related to each study drug, and CTCAE Grade  $\geq 3$  treatment-related TEAE, along with CTCAE grades. After study drug treatment, each TEAE, SAE, TEAE of special interest, immune-related TEAE, and possible liver injury event, along with CTCAE grade, in each cohort will be summarized by SOC and PT, and each treatment-related TEAE and SAE related to study drugs will be summarized by SOC and PT. Immune-related AE will also be summarized by immune-related category and PT. The incidence of AE is calculated based on the number of subjects having an AE, instead of the number of AE episodes. For TEAE occurring after the start of study treatment, causality with study drugs consists of definitely related, possibly related, and indeterminable; if causality is missing, the TEAE will be considered drug-related for analysis. TEAE with CTCAE grade missing will be counted as missing.

TEAE of special interest includes the following:

- Grade  $\geq 3$  infusion reaction;
- Grade  $\geq 2$  diarrhea/colitis, uveitis, and interstitial pneumonia;
- Other Grade  $\geq 3$  immune-related AE;
- Grade 4 amylase or lipase increased.

Each AE, TEAE leading to dose interruption or modification, TEAE leading to treatment withdrawal, severe TEAE, and death will be listed.

For immune-related TEAE (classified by immune-related TEAE), the descriptive summary of the number and percentage of subjects have received corticosteroids or immunomodulators, received immunomodulators, received corticosteroids (further divided into systemic and topical administration), and received high-dose corticosteroids (defined as at least one dose or daily dose of  $\geq 40$  mg prednisone or equivalent; further divided into systemic and topical administration), and the starting dose and duration of high-dose corticosteroids will also be provided. The dosage of different hormonal drugs will be converted into the equivalent dose of prednisone according to the following formula: 0.75mg of dexamethasone = 5 mg of prednisone = 4mg of methylprednisolone = 20mg of hydrocortisone = 0.8mg of betamethasone.

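### Protocol 7.2.5 contradicts itself on whether endocrine events count as immune-mediated AEs, and the SAP does not settle it, so the immune-related count may be understated

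*Protocol*

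**What the plan says.** Protocol 7.2.5 makes three statements in succession.

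- The first sentence defines an IMAE through a list of event types that ends with "nephritis/renal dysfunction, rash, and endocrinopathy) related to immunosuppressive treatment". Endocrine events are in.
- The second sentence names five endocrine types (adrenal insufficiency, diabetes, hypophysitis, hyperthyroidism, hypothyroidism/thyroiditis) and says that they "are often excluded, as they are usually unrelated to treatment and are usually managed in the absence of interventions with immunosuppressants".
- Table 11 is titled "Preferred terms included in the IMAE analysis to support warnings and precautions". It has ten rows, and five of them are those same endocrine types. The diabetes row, for example, reads "Diabetes mellitus, diabetic ketoacidosis". The hypothyroidism/thyroiditis row lists only acute and autoimmune thyroiditis as PTs; Hypothyroidism is not among them.

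SAP 11.4.1 plans summaries of immune-related TEAEs by SOC, PT and grade, and of corticosteroid and immunomodulator use for those events. It adds: "Immune-related AE will also be summarized by immune-related category and PT". It does not define the term, list PTs or refer to Table 11. Protocol 7.2.7 and SAP 11.4.1 both make other immune-related events of Grade 3 or higher a special-interest item, again without a definition.

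**The concern.** The three statements in 7.2.5 cannot all be followed, and both reasons given for exclusion are weak. The first, that endocrine events are mostly not caused by treatment, is contradicted elsewhere in the protocol. The second, that they are usually handled without immunosuppressants, explains why immunosuppressant use should not be a condition for counting them. It does not explain leaving them out.

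At stake is a planned safety summary, and possibly a special-interest category that must be reported to the sponsor within 24 hours (Protocol 7.4.4). In an open-label trial, an inclusion rule that is still open when the tables are built can be settled after the data have been seen. The possible error also runs one way: leaving endocrine events out can only lower the immune-related rate.

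**Working it through.** **1. Is the stated reason consistent with the rest of the protocol?**

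| Place | How it treats endocrine events |
|---|---|
| 7.2.5, second sentence | Usually not treatment-related, often left out |
| 1.1.1.5 | Hypophysitis and both hypo- and hyperthyroidism are among reactions possibly related to SHR-1210 |
| 1.3.1 | Hypothyroidism is among the most common treatment-related AEs, 5.6% of 539 patients |
| 1.3.1 | Reactions needing special attention include "immune-related interstitial pneumonia, rash, thyroiditis", with adrenal insufficiency among the rarer ones |
| Table 7 (immune-related toxicity) | Rows for type 1 diabetes, hyperthyroidism, hypothyroidism and hypophysitis |
| Appendix 4, part 4 | A section on endocrine events within the immune-related AE guidance |

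It is not consistent. Every other place treats these events as related to the drug, immune in origin, or both.

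**2. Check of the 5.6%.** The numerator is not stated. 0.056 × 539 = 30.2. Of the whole-number counts, 29/539 = 5.4%, 30/539 = 5.6% and 31/539 = 5.8%, so 30 is the only one that rounds to 5.6%. In the same paragraph, 414/539 = 76.8% reproduces as printed.

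**3. What each reading of 7.2.5 does.**

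| Reading | Hypothyroidism | Other endocrine types |
|---|---|---|
| Second sentence applied | out | out |
| Table 11 applied PT by PT | out (PT not listed) | in |
| Table 11 applied by row heading | in | in |

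The loss of hypothyroidism therefore has two separate causes. Deleting the second sentence alone would not cure the second reading.

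**4. Scale for hypothyroidism under either of the first two readings.** Assume that the 5.6% carries over to this trial. Expected subjects = n × 0.056.

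- Both cohorts: 98 × 0.056 = 5.5
- Cohort 1: 43 × 0.056 = 2.4
- Cohort 2: 55 × 0.056 = 3.1
- With the 10% allowance for non-evaluable subjects (48 + 62 = 110): 110 × 0.056 = 6.2

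The chance of at least one such subject among 98 is 1 − (1 − 0.056)^98 = 0.996, so under that assumption the question will almost certainly arise.

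The expected effect of hypothyroidism on overall immune-related incidence is at most 5.6 percentage points. It is smaller where an affected subject has another immune event and is counted anyway. The documents give no rate for the other four endocrine types on SHR-1210, so no figure is offered for them.

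**The case against.** A reader might infer that the plan excludes endocrine events and that immune-related incidence is therefore undercounted. The documents do not support that. The sentence says often, not always. Table 11, the stated list for the analysis, keeps five endocrine rows, and the SAP excludes nothing. A specific analysis list would normally prevail over a loose descriptive sentence. The paragraph can even be read as waiving an immunosuppressant requirement for endocrine events rather than removing them. All of this stands against a claim of certain undercounting. It does not remove the contradiction: a word such as often, with no statement of when it applies or who decides, leaves the matter to judgement event by event.

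Three further points limit the finding.

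- Every TEAE is tabulated by SOC and PT, as are those related to each study drug. Hypothyroidism would appear there, and only its immune-related label is at risk. This stands.
- The special-interest item may be wider than 7.2.5. It uses the term immune-related, not immune-mediated, and follows an entry naming uveitis, which Table 11 lacks. So it is not shown that this item would lose endocrine events. This stands too, and is a reason to state the point explicitly.
- The 5.6% comes from a pool of monotherapy and combination use across advanced cancers. It gives scale and is not a forecast.

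**Conclusion.** The point holds as an unresolved contradiction that allows an undercount. The documents do not establish that one will occur. Protocol 7.2.5 includes endocrine events in its first sentence and in five of ten table rows, and discounts them in between for a reason that the protocol's own data contradict. The SAP does not say which text governs.

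If the second sentence is applied, or Table 11 is read PT by PT, and if the 5.6% rate carries over, about 5.5 of 98 subjects with treatment-related hypothyroidism would lack the immune-related label (2.4 of 43 and 3.1 of 55 by cohort). If Table 11 is applied by row heading, none would be lost for this reason. A safety sub-classification is affected, not the primary endpoint or AE collection. The correction is still worth making before database lock, because the ambiguity can only favour the drug.

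**What to change.** 1. In Protocol 7.2.5, replace the second sentence with: Endocrine events (adrenal insufficiency, diabetes, hypophysitis, hyperthyroidism and hypothyroidism/thyroiditis) are included in the IMAE analysis whether or not immunosuppressants were given.
2. In Table 11, add the PT Hypothyroidism to the hypothyroidism/thyroiditis row.
3. In SAP 11.4.1, define immune-related TEAEs by citing this rule and one final PT list, and state that endocrine events count toward the special-interest item for other immune-related events of Grade 3 or higher.

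The cost is one protocol sentence, one table entry and a short SAP addition. No new data are needed. The reported immune-related AE rate may become slightly less favourable.

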7.2.6 Potential drug-induced liver injury

Drug-induced liver injury will be considered if AST and/or ALT levels are abnormal accompanied with abnormal elevation of total bilirubin, the following criteria are met, and when there are no other causes of liver injury. These cases should always be considered as important medical events and reported as SAEs.

Potential drug-induced liver injury is defined as follows (Table 12):

Baseline Period	Normal (AST/ALT and TBIL)	Abnormal (AST/ALT and TBIL)
Treatment period	
ALT or AST $\geq 3 \times$ ULNwith TBIL $\geq 2 \times$ ULNand ALP $\leq 2 \times$ ULNand no hemolysis	
AST or ALT $\geq 2 \times$ baseline level, and $\geq 3 \times$ ULN; or AST or ALT $\geq 8 \times$ ULNwith TBIL increase $\geq 1 \times$ ULN or $\geq 3 \times$ ULN

Table 12. Definition of potential drug-induced liver injury

After being notified of the abnormal results, the subjects should return to the study center for an assessment as soon as possible (preferably within 48 h). Assessments include the laboratory tests, detailed medical history, and physical assessment, and the possibility of hepatic tumor (primary or secondary) should be considered.

Except for the reexaminations of AST and ALT, albumin, creatine kinase, TBIL, direct and indirect bilirubin, γ -GT, prothrombin time (PT)/international normalized ratio (INR), and ALP should also be examined. Detailed medical history should include history of alcohol use,

acetaminophen, soft drugs, various supplements, family diseases, occupational exposure, sexual behavior, travel, contact with jaundice patients, surgery, blood transfusion, hepatic diseases, and allergies. Further tests may include the testing for acute hepatitis A, B, C and E, and hepatic imaging (such as biliary tract). If the above laboratory criteria are confirmed upon re-examination, the possibility of potential drug-induced liver injury should be considered in the absence of any other causes of abnormal liver function, without waiting for all liver function test results. Potential drug-induced liver injury should be reported as an SAE.

7.2.7 Adverse Events of Special Interest

Special interest events include the following:

- Grade ≥ 3 infusion reactions;
- Grade ≥ 2 diarrhea/colitis, uveitis, and interstitial pneumonia;
- Grade ≥ 3 other immune-related AEs;
- Grade 4 amylase or lipase increased.

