Blood Sampling for ADA Detection ^[19]			x ^[20]	x ^[20]	x	x	
Adverse Events ^[20]	x	x	x	x	x	x	x
Concomitant Medications/Concomitant Treatments ^[21]	x	x	x	x	x	x	

Note: Other than the examinations and time points listed in the table, the investigator may add visits and other examinations if needed. Results should be documented in the corresponding sections of the electronic case report form (eCRF) (e.g., "Unscheduled Visit Examination").

- [1] Except for tumor imaging evaluation and tumor tissue biopsies performed within the specified time limit prior to the first dose, written informed consent must be obtained from subjects before any study procedures. Subjects who have failed previous screening may be screened again in this study. The informed consent form must be re-signed and a new subject number should be given for re-screening.
- [2] Medical history and treatment history: including tumor history (diagnosis, surgery, radiotherapy, chemotherapy history) and history of other concurrent diseases. Among them, tumor diagnosis should include: the results of the histological diagnosis, pathological classification, histological grade, clinical stage, and time of first diagnosis prior to enrollment.
- [3] ECOG PS: The ECOG PS is evaluated within 7 days prior to the first dose, before drug administration on Day 1 of each cycle, at the end of treatment/upon withdrawal, and upon the first visit during the safety follow-up period.
- [4] Vital signs: Pulse rate, respiratory rate, body temperature and blood pressure; the vital signs are evaluated within 7 days prior to the first dose, before drug administration on Day 1 of each cycle, at the end of treatment/upon withdrawal, and upon the first visit during the safety follow-up period.

- [5] Physical examination: Within 7 days prior to the first dose and at the end of treatment/upon withdrawal, a comprehensive physical examination (including general condition, head and face, skin, lymph nodes, eyes, ears, nose and throat, mouth, respiratory system, cardiovascular system, abdomen, reproductive and urinary system, musculoskeletal system, nervous system and mental state) is performed; before drug administration on Day 1 of each cycle and upon the first visit of the safety follow-up period, symptom-directed physical examination can be performed if clinically indicated.

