- [6] Virology: HBsAg, HBsAb, HBeAg, HBeAb, HBcAb, HBV DNA (if the Hepatitis B five items test indicates HBV infection [HBsAg positive] or if the subjects have a history of HBV infection, HBV DNA quantification should be performed), HCV-Ab (if the result is positive, HCV RNA quantification should be performed), and HIV-Ab.
- [7] Hematology: Red blood cell count (RBC), hemoglobin (Hb), platelet count (PLT), white blood cell count (WBC), absolute neutrophil count (ANC), and lymphocyte count; hematology test is performed within 7 days prior to the first dose, before drug administration on Day 1 of each cycle, at the end of treatment/upon withdrawal, and upon the first visit of the safety follow-up period.
- [8] Urinalysis: WBC, RBC, and urine protein. If the urine protein $\geq 2+$, the 24-h urine protein quantification should be performed; the urinalysis is performed within 7 days prior to the first dose, before drug administration on Day 1 of every two cycles, at the end of treatment/upon withdrawal, and upon the first visit during the safety follow-up period.
- [9] Fecal occult blood test: Fecal occult blood test is performed within 7 days prior to the first dose (if the fecal occult blood is positive, the test should be performed again. If the result is still positive, gastrointestinal endoscopy should be performed), before drug administration on Day 1 of every two cycles, at the end of treatment/upon withdrawal, and upon the first visit during the safety follow-up period.
- [10] Blood biochemistry: Alanine transaminase (ALT), aspartate aminotransferase (AST), gamma-glutamyl transferase (γ -GT), total bilirubin (TBIL), direct bilirubin (DBIL), alkaline phosphatase (AKP), blood urea nitrogen (BUN, preferred) or urea, total protein (TP), albumin (ALB), creatinine (Cr), blood glucose (GLU), K^+ , Na^+ , Ca^{2+} , Mg^{2+} and Cl^- . The blood biochemistry test is performed within 7 days prior to the first dose, before the drug administration on Day 1 of each cycle, at the end of treatment/upon withdrawal, and upon the first visit of the safety follow-up period.
- [11] Coagulation function: Activated partial thromboplastin time (APTT), prothrombin time (PT), thrombin time (TT), fibrinogen (FIB), and international normalized ratio (INR); coagulation function is evaluated within 7 days prior to the first dose, before drug administration on Day 1 of each cycle, at the end of treatment/upon withdrawal, and upon the first visit during the safety follow-up period.

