The following screening procedures should be completed within 7 days prior to the start of the study treatment. A pregnancy test should be completed within 72 hours prior to the start of the study treatment.

- ECOG PS.
- Vital signs: pulse, respiratory rate, body temperature, and blood pressure.

- Comprehensive physical examination: general condition, head and face, skin, lymph nodes, eyes, ears, nose and throat, oral cavity, respiratory system, cardiovascular system, abdomen, reproductive-urinary system, musculoskeletal system, nervous system, mental state, etc.;
- Hematology: Red blood cell count (RBC), hemoglobin (Hb), platelet count (PLT), white blood cell count (WBC), absolute neutrophil count (ANC), and lymphocyte count.
- Urinalysis: WBC, RBC, and urine protein. If urine protein is $\geq 2+$, then a quantitative 24-h urine protein test should be added.
- Fecal occult blood (OB) test: Fecal occult blood test is performed within 7 days prior to the first dose (if the fecal occult blood is positive, the test should be performed again. If the result is still positive, gastrointestinal endoscopy should be performed), on Day 1 of every two cycles, at the end of treatment/upon withdrawal, and upon the first visit during the safety follow-up period.
- Blood biochemistry: Alanine transaminase (ALT), aspartate aminotransferase (AST), gamma-glutamyl transferase (γ -GT), total bilirubin (TBIL), direct bilirubin (DBIL), alkaline phosphatase (AKP), blood urea nitrogen (BUN, preferred) or urea, total protein (TP), albumin (ALB), creatinine (Cr), blood glucose (GLU), K^+ , Na^+ , Ca^{2+} , Mg^{2+} and Cl^- .
- Thyroid function: Including serum thyroid stimulating hormone (TSH), free triiodothyronine (FT3), and free thyroxine (FT4). If FT3 and FT4 cannot be obtained, T3 and T4 are allowed for substitution;
- Coagulation function: Activated partial thromboplastin time (APTT), prothrombin time (PT), thrombin time (TT), fibrinogen (FIB), and international normalized ratio (INR).
- 12-Lead ECG: Attention should be paid to QT, QTc, and PR-intervals. The investigator may decide to add other investigations if the results are abnormal.
- Echocardiography: Including left ventricular ejection fraction (LVEF) assessment. Echocardiography is performed once within 7 days before the enrollment. After that, echocardiography is performed if clinically indicated and at the end of treatment/upon withdrawal.

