7.2 Safety Evaluation

7.2.1 Safety endpoints

Safety parameters for this study include clinical symptoms, vital signs, physical examination, laboratory tests (hematology, urinalysis, blood biochemistry, thyroid function, and coagulation function). AEs are evaluated according to NCI CTCAE Version 4.03, including type, incidence, severity, start and end date, whether it is an SAE, causality with the study drugs, and outcome.

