7.4.4 Reporting of Special Interest Events

For SIEs specified in the study protocol, the investigator must complete the "Report of Special Interest Event for Hengrui Clinical Studies" and report to the sponsor within 24 hours of knowing of the event.

If the SIE is also an SAE, the "NMPA Serious Adverse Event Report Form" should also be completed and reported to the relevant authorities according to the SAE reporting procedure.

SIEs are shown in section [7.2.7](#).

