### **11.4.7 Other safety data**

Examinations such as echocardiography, virology, fecal occult blood, pregnancy, and coagulation function will be listed.

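### Grade 4 amylase or lipase increase is a special-interest event, but no scheduled test measures either enzyme, so untested subjects count as event-free

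*Protocol*

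**What the plan says.** Protocol section 7.2.7 lists four groups of special-interest events. The last is "Grade 4 amylase or lipase increased", and SAP section 11.4.1 repeats it. Under Protocol section 7.4.4 the investigator must "report to the sponsor within 24 hours of knowing of the event".

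The blood chemistry panel is enumerated twice. Note 10 to the Schedule of Activities names the liver tests and continues with "blood urea nitrogen (BUN, preferred) or urea, total protein (TP), albumin (ALB), creatinine (Cr), blood glucose (GLU" and five electrolytes. The screening list in Protocol section 6.1 is the same: "alkaline phosphatase (AKP), blood urea nitrogen (BUN, preferred) or urea, total protein (TP), albumin (ALB), creatinine (Cr), blood glucose (GLU" and the same electrolytes. Neither list contains amylase or lipase. Later visits (Protocol sections 6.2, 6.3 and 6.4.1) refer back to clinical chemistry without adding analytes.

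Protocol section 7.2.1 gives the laboratory safety parameters as "laboratory tests (hematology, urinalysis, blood biochemistry, thyroid function, and coagulation function", with no pancreatic category. SAP section 11.4.7 adds only this: "Examinations such as echocardiography, virology, fecal occult blood, pregnancy, and coagulation function will be listed". The note under the Schedule of Activities says that "the investigator may add visits and other examinations if needed".

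For the analysis, SAP section 11.4 uses the safety set by cohort. SAP section 11.4.1 states that each "TEAE of special interest, immune-related TEAE, and possible liver injury event, along with CTCAE grade, in each cohort will be summarized", and it counts subjects with an event. Protocol section 7.3.2 takes all subjects evaluated for safety as the denominator of adverse event incidence.

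**The concern.** This event is defined entirely by a laboratory value. Most of the other named special-interest events can present with symptoms; an enzyme rise need not. If the enzyme is not measured, the event does not exist in the data.

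Three things are at stake:

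- **Incidence.** Entry to the safety set (SAP section 6.3) needs one dose and some post-dose safety data, not an enzyme result. SAP section 10.2 imputes nothing. An untested subject is therefore in the denominator and cannot be in the numerator.
- **Baseline.** A treatment-emergent event in the SAP is one that appears or worsens after the first dose. Without a scheduled pre-dose value, a raised enzyme found later cannot reliably be separated from one already present.
- **Expedited reporting.** If no test is done, the site may never learn of the event and the 24-hour clock may never start.

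Laboratory abnormalities are part of a named secondary endpoint (Protocol section 2.2), so this touches a declared objective.

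**Working it through.** The plan states no rate, precision or sample size for this event, so there is no figure to reproduce. The main check compares the event list with every laboratory list.

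**Step 1: is either enzyme scheduled?**

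| Place | Content | Amylase or lipase? |
|---|---|---|
| Schedule of Activities, note 10 | ALT, AST, γ-GT, total and direct bilirubin, AKP, BUN or urea, total protein, albumin, creatinine, glucose, K, Na, Ca, Mg, Cl | No |
| Protocol 6.1 | Same list | No |
| Protocol 6.2, 6.3, 6.4.1 | Clinical chemistry, not redefined | No |
| Protocol 7.2.1 | Five laboratory categories | No |
| SAP 11.4.2, 11.4.7 | Hematology, biochemistry, urinalysis; other examinations | No |
| Protocol 7.2.7, SAP 11.4.1 | Special-interest list | Yes, as the event only |

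Scheduled measurements per subject: zero, including at baseline.

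**Step 2: does anything else prompt a test?** Protocol Table 7 and Appendix 4 have no entry for amylase, lipase or pancreatitis. By contrast, potential drug-induced liver injury (Protocol section 7.2.6), also laboratory-defined, rests on ALT, AST, total bilirubin and alkaline phosphatase, all in the panel. Where that section needs an extra analyte, creatine kinase, it asks for it. The enzyme event has neither arrangement.

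**Step 3: what would an empty row imply?** With 0 events in n tested subjects, the exact (Clopper-Pearson) two-sided 95% upper limit is 1 − 0.025^(1/n). The target cohort sizes are 43 and 55.

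- Cohort 1, all tested: 1 − 0.025^(1/43) = 8.2%.
- Cohort 2, all tested: 1 − 0.025^(1/55) = 6.5%.
- At the enrolment figures of 48 and 62: 7.4% and 5.8%.

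The number tested is not in the documents. If, by assumption, a quarter were tested (11 and 14 subjects), the limits become 28.5% and 23.2%. If a tenth were tested (4 and 6), they become 60.2% and 45.9%. Even these treat the tested subjects as representative, which ad hoc testing does not ensure.

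**Step 4: how easily could true events be missed?** Let p be the true incidence and f the share of events detected. The chance of recording none is (1 − p·f)^n. Both p and f are assumptions.

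| Detection f | Cohort 1 (n = 43), p = 3% | Range, p = 2% to 5% | Cohort 2 (n = 55), p = 3% | Range, p = 2% to 5% |
|---|---|---|---|---|
| 1 | 27% | 42% to 11% | 19% | 33% to 6% |
| 0.25 | 72% | 81% to 58% | 66% | 76% to 50% |
| 0.10 | 88% | 92% to 81% | 85% | 90% to 76% |

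For example, cohort 1 with f = 0.25: (1 − 0.03 × 0.25)^43 = 0.9925^43 = 0.72.

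**The case against.** The best defence is that a special-interest list may be a reporting trigger and not a screening list. Uveitis is on the same list, and no eye test is scheduled beyond the general physical examination. Creatine kinase is requested only when liver injury is suspected. Unscheduled tests are allowed and recorded, and Protocol section 7.2.2 makes clinically significant laboratory findings adverse events. So a detection route exists, and a reader who inferred that the event cannot be detected at all would go too far. The defence does not remove the gap: uveitis can announce itself clinically, creatine kinase has a stated trigger, and the enzyme event has no trigger.

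Three further inferences are tempting and not supported:

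- **That reports must be late.** The 24 hours run from awareness, so an event found by an unscheduled test can be reported on time. The problem is finding the event.
- **That a pooled 0/98 will be presented, with an upper limit of 3.7%.** The SAP summarises by cohort, and cohort 1 also by treatment stage. It plans no pooled table, no confidence limit for safety counts, and no explicit zero row for each component.
- **That most subjects will go untested, that the rate will be near zero, or that it will be read as proof of safety.** The documents give no testing frequency, no expected rate and no such interpretation.

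It also stands that dividing by tested subjects alone would not cure the problem. If tests follow clinical suspicion, that rate would tend to overstate incidence among treated subjects.

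**Conclusion.** The mismatch is real. A special-interest event defined by two enzymes is paired with a schedule that measures neither, and the planned summary counts untested subjects as event-free. The incidence may be understated; by how much cannot be known, because neither the testing frequency nor the true rate is given. The cohort limits of 8.2% and 6.5% show what an empty row would suggest, and they are valid only if all 43 and 55 subjects were tested.

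The point is confined to safety ascertainment. Response rate, error rate, power and sample size are untouched. It is worth correcting because the plan, followed exactly as written, cannot assess the event systematically and the remedy is small.

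**What to change.** **Protocol.** Reconcile section 7.2.7 (and SAP 11.4.1) with note 10 of the Schedule of Activities and section 6.1. The simplest way is to add amylase and lipase to the biochemistry list, on blood already drawn and including the baseline sample. This concerns measurement only and implies nothing about how a raised value is managed. The cost is two extra assays per sample, with no extra visit or draw. If it is introduced mid-trial, earlier and later subjects will be ascertained differently, and the report should say so. That is a live issue: version 6.0 is dated August 2018 and last enrolment was expected in December 2018.

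**SAP 11.4.1, whether or not the panel changes.** For this event:

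- Keep the safety set as denominator.
- Beside it, report the number of subjects per cohort with at least one post-baseline amylase or lipase result.
- Label the event as not systematically assessed wherever testing was ad hoc.
- Do not use ad hoc tested subjects as the only denominator.

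The cost is one column and one footnote, plus the work of collecting unscheduled results. The SAP is to be final before database lock, so this can be specified in advance.
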